## I. Hypotheses and Specific Aims:

**HYPOTHESIS:** In obese adolescents, delayed melatonin onset and offset will correlate with insulin resistance (IR), and may be affected by sex.

### SPECIFIC AIMS:

**Aim 1:** Establish a method to measure and model the melatonin profile, including melatonin onset and offset, as a marker of circadian rhythm in obese adolescents.

**Aim 2:** Develop a physiologically-based mathematical model of adolescent human sleep/wake and circadian interactions, and apply the model to investigate the mechanisms associated with published changes in sleep/wake behavior observed in adolescent sleep as well as in individual subjects.

**Aim 3:** Relate the timing of melatonin onset and offset to measures of insulin resistance in obese adolescents and examine sex differences among these variables.

## Research Methods

### Outcome Measure(s):

Primary Outcomes: Melatonin phase assessment and IR

Melatonin phase assessment: During the study visit, subjects will be admitted to the Children's Hospital Clinical research center inpatient unit at 4PM on Wednesday, Thursday or Friday. The profile of melatonin release will be assessed at the study visit using a serial saliva sampling method from 5PM on Thursday or Friday to 12PM the following day. Saliva (~2mL) will be collected in 30 or 60 minute intervals in dim light (<10 lux in the room; ~1.9 lux in the angle of gaze, confirmed by light meter) using polystyrene tubes throughout the night. Individualized melatonin sampling schedules will be determined to optimize calculation of DLMOOn and DLMOOff times by introducing 30 minute sampling at the times at which DLMOOn and DLMOOff are predicted to occur based on actigraphy-reported sleep, wake, and midsleep times.

Assessment of IR: During the screening visit, a 3-hour frequently sampled OGTT will be performed in the outpatient CTRC. The OGTT will take place in the AM, after a fast of at least 10 hours. A 20-gauge iv catheter will be inserted in the antecubital vein for blood sampling. After baseline samples are collected, a 3-hour OGTT with 75 mg dextrose drink will be performed. Glucose and insulin samples will be collected every 30 minutes. In addition, we will assess fasting labs to check for other components of metabolic syndrome including hemoglobin A1C for dysglycemia, ALT/AST for liver inflammation, sex hormone binding globulin as a marker of IR, cholesterol panel, CRP as a marker of inflammation, leptin as a gut hormone known to influence hepatic IR, and adiponectin, thought to influence adipose IR. Additionally, blood pressure will be taken to assess for hypertension and waist/hip ratio will be measured as a marker of metabolic disease.

Additional Measures: Questionnaires assessing additional sleep parameters, mood/behavior, and diet/activity will be completed by participants to identify variables to control for in analyses (e.g. presence of symptoms of sleep-disordered breathing) and/or utilize in exploratory analyses (e.g., relationship between sleep and diet/activity).

- i. The **Morningness/Eveningness Scale for Children**  and the **Munich Chronotype Questionnaire for Children**  will be used to determine chronotype (diurnal preference).

- ii. The **Cleveland Adolescent Sleepiness Questionnaire**, **Sleep Disturbances Scale for Children/Adolescents**, and the **Adolescent Sleep Hygiene Scale** will be completed by participants to obtain information on behavioral sleep variables, including daytime sleepiness and sleep-promoting and inhibiting factors.
- iii. The **Strengths & Difficulties Questionnaire**, an adolescent self-report tool, will be used to assess symptoms of mood and behavior problems.
- iv. The **Profile of Mood States 2 Short Version**, an adolescent self-report measure of mood, completed on the computer.
- v. The **Three Day Physical Activity Recall** (3DPAR^10), a questionnaire asking youth to recall their physical activity levels from the previous three days, will be completed. Physical activity can directly affect insulin sensitivity, our primary outcome measure.
- vi. Macronutrient intake pattern will be ascertained using the **SEARCH Food Frequency Questionnaire**, devised to include common food choices among ethnically and regionally diverse youth aged 10-19 years. The instrument is self-administered with staff support to provide instructions, answer questions, and to review the form after completion, and captures the last week of dietary intake.
- vii. Psychomotor Vigilance Task, a computerized test of sustained attention with particular sensitivity to sleepiness.

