### **Study Design and Research Methods**

Study Timeline: Participants will have 3 visits: an initial visit, a screening visit, and an overnight study visit. The initial visit will include informed consent and assent and receiving an actigraphy watch and instructions. The screening visit will include questionnaires, 3-hour frequently sampled oral glucose tolerance test (OGTT), and fasting labs to check for other components of metabolic syndrome. During the overnight study visit subjects will be admitted to the Children's Hospital Clinical research center inpatient unit from 4PM Thursday or Friday to 12PM the following day for salivary melatonin collection. During the entire protocol, teens will be asked to abstain from caffeine, non-steroidal anti-inflammatory drugs, marijuana, high carbohydrate meals, and alcohol.

Initial visit and sleep/wake monitoring: The initial visit will last approximately 30 minutes and will include consent and assent. Participants will be provided an actigraphy watch to monitor typical home sleep patterns. The Spectrum sleep/wake monitor (Phillips Resperonics, Bend, OR) will be worn on the non-dominant wrist and will collect data on movements in 1-min bins. The watch will be worn for the 7 days preceding the initial visit and participants will complete a concurrent sleep diary emailed to them each morning via RedCap to allow for removal of artifacts (e.g., failure to wear the actigraphy watch during a portion of the night). If participants have not completed the sleep diary by mid-morning, a RedCap email and text message reminder will be sent. The text messages will be generic so as not to identify the participant or that they are part of a research study. If participants do not have email or computer access, they can complete a paper/pencil sleep diary.

Screening visit and sleep/wake monitoring: The screening visit will last approximately 4 hours and will ideally occur on Thursdays or Fridays in order to be consistent with the amount of accumulated sleep debt incurred over the week. Menstruating girls will be scheduled in the follicular phase when possible, as menstrual timing can influence measures of IR. Participants will receive or be mailed an actigraphy watch to wear for 7 days prior to the overnight study visit while filling out a concurrent sleep diary.

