### **Description, Risks and Justification of Procedures and Data Collection Tools:**

#### **1. Blood Sampling**

**Description:** Blood will be drawn using a peripheral IV for HbA1c, ALT/AST, sex hormone binding globulin, a cholesterol panel, CRP, leptin, and adiponectin, and OGTT.

**Risk:** Minimal. Risk of pain, bruising at site of blood draw, excessive amount of blood

**Minimizing Risk:** The study involves sampling blood at multiple time points, thus an IV is needed to avoid multiple needle sticks. Proper sterile techniques will be used with blood draws and IV placement to decrease infection risk. EMLA cream will be used if subject desires to minimize pain of IV. The routine guidelines in our Pediatric CTRC are 2.5ml/kg for a single draw and no more than 5ml/kg over a 4 week period. For this study, the baseline labs will include 13 ml of blood and the OGTT includes 29ml of blood. Thus, our study visit is within the NIH Clinical Center guidelines of 9ml/kg in 6-8 weeks and within Children's Hospital Colorado's institutional guidelines of 5 ml/kg. We will use a minimum weight cutoff of 38 kg to remain below the most conservative pediatric CTRC blood drawing guidelines. Finally, our CTRC has a system to track other studies subjects might enroll in, and we ask during our consent process if the subject has been involved in any other studies in the past 6 weeks to avoid excessive blood drawing.

**Justification:** These labs are to measure for components of the metabolic syndrome, and to assess the primary study endpoint, IR. A hemoglobin A1c can be used to rule out diabetes.

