#### **2. Oral Glucose Tolerance Test (OGTT)**

**Description:** An OGTT will be performed with multiple blood draws over 3 hours. The purpose of the OGTT is to provide a controlled oral stimulus to effect changes in lipolysis and hepatic glucose release.

**Risk:** The subjects rarely experience nausea within 15 min of consuming the drink, however, the amount of carbohydrate is very similar to a large soda, which is regularly consumed by this patient population.  
**Justification/Minimization:** A standard oral challenge is needed to study insulin resistance in order to examine the relationship with sleep. Our team of investigators, CTRC pediatric research nursing staff and physicians are well experienced with the OGTT blood draw procedure. A floor nurse located on the 9th floor of CHC will be available during our inpatient visits and patients will be distracted by TV or other similar means during the OGTT, to minimize queasiness.

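### The stated 75 mg dextrose load for the OGTT conflicts with the protocol's own comparison of the drink to a large soda

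*Combined protocol and SAP*

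**What the plan says.** Outcome Measure(s) lists "Primary Outcomes: Melatonin phase assessment and IR". Its Assessment of IR paragraph sets out the test: a morning visit after an overnight fast, an intravenous line, baseline samples, and then "a 3-hour OGTT with 75 mg dextrose drink will be performed". It adds that "Glucose and insulin samples will be collected every 30 minutes".

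Item 2 of the procedures and risks section, Oral Glucose Tolerance Test (OGTT), describes the drink again. Its purpose is to "provide a controlled oral stimulus to effect changes in lipolysis and hepatic glucose release". Under Risk, the reader is told that "the amount of carbohydrate is very similar to a large soda, which is regularly consumed by this patient population". Under Justification/Minimization, the reason given is that "A standard oral challenge is needed to study insulin resistance in order to examine the relationship with sleep".

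Item 1, Blood Sampling, says the laboratory tests serve in part "to assess the primary study endpoint, IR". In the Data Analysis Plan, the Aim 3 text on calculating insulin resistance derives the Matsuda index from the glucose and insulin values over time.

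**The concern.** The methods paragraph and the risk paragraph describe one drink in terms that do not fit together. The methods paragraph gives a quantity of less than a tenth of a gram. The risk paragraph gives an everyday comparison that implies far more.

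The quantity is an operative part of the protocol. It sets the size of the stimulus whose glucose and insulin response becomes the Matsuda index, and Aim 3 relates that index to melatonin onset and offset. The exploratory insulinogenic and disposition indices depend on it too, since they use changes at 30 minutes after the drink. If the stated figure were followed literally, those measures would not reflect the challenge that item 2 describes. There is also a consistency point: item 2 is the risk description for a study that enrols minors, so it should describe the same drink as the methods.

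**Working it through.** **Do the two passages describe the same drink?** Both describe a 3-hour OGTT with repeated blood draws. Study Design and Research Methods schedules one OGTT, at the screening visit, and the compensation paragraph likewise attaches one OGTT to that visit. Item 2 mentions a nurse available at inpatient visits, whereas the methods place the test in the outpatient unit, but no second OGTT appears anywhere. The two passages therefore refer to the same drink.

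**Does any other text settle the load?** The compensation paragraph, the study timeline, item 1 (Blood Sampling) and the Aim 3 calculations all refer to the OGTT or its results, and none gives a load. The methods figure is the only number. It stands in a complete sentence of running prose, with no sign of redaction or a broken table.

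**Conversion.** 75 mg ÷ 1000 = 0.075 g.

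**Size of the conflict.** The documents give no carbohydrate content for a large soda, so the following contents are assumptions. The ratio is the assumed content in grams ÷ 0.075 g.

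| Assumed soda carbohydrate | Ratio to the stated load |
|---|---|
| 1 g (implausibly low) | 13 |
| 10 g | 133 |
| 25 g | 333 |
| 40 g | 533 |
| 100 g | 1333 |

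For the two statements to agree, a large soda would have to contain about 0.075 g of carbohydrate. The conflict therefore does not depend on which value in the range is chosen. The range only tests the contradiction; it does not indicate what the load should be.

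**What the line governs.** Taking the 30-minute interval across the full 3 hours, 180 min ÷ 30 min = 6 sampling times after the drink. With one baseline time, that is 7 per participant, so 6 of 7 follow the drink. At the maximum enrolment of 30, 6 × 30 = 180 post-drink sampling times. This count shows how much of the test rests on the specification. It is not an estimate of bias.

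**The case against.** The strongest reply is that this is a drafting slip in one phrase. Item 2 describes a standard challenge run by staff with experience of the test, so nobody is likely to give the amount as printed. Most of the test is well specified: setting, fasting, substance, duration, sampling interval, analytes and derived index. Only the quantity is in doubt, no effect on results has been shown, and on that view the point is minor.

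Much of this stands. Literal use is unlikely, and the rest of the test description is adequate. It is also fair to say that the soda line is a lay comparison without a number, that the phrases about a standard challenge and a controlled stimulus state no amount, and that a count of samples does not measure the discrepancy. The count further assumes one baseline time, a final sample at 3 hours and full enrolment.

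What does not stand is the inference that the text can be left alone. The quantity is the one element that cannot be recovered from the document, because the only number given is the one in conflict. Readers should not have to override a protocol's sole stated figure to learn the stimulus for a primary outcome. The missing soda figure does not rescue the text either, since the conflict remains even at 1 g.

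**Conclusion.** The concern holds. The 0.075 g stated in the methods and the soda comparison in item 2 are incompatible descriptions of the same drink, by a factor of about 333 to 1333 on an assumed soda content of 25 to 100 g and about 13 even at 1 g. The conclusion rests on two points: the document schedules only one OGTT, and a large soda contains far more than 0.075 g of carbohydrate.

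The documents do not show which description is intended, and neither is taken here as correct. A unit slip is one possible explanation, but nothing in the text confirms it.

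The point should be fixed because the line specifies the test behind a primary outcome. Its practical reach is limited: insulin resistance is affected only if the figure is followed as written. The melatonin phase measures (Aim 1), the sleep/wake model (Aim 2), the fasting laboratory tests, the sample size of 30 and the power statement for a correlation of 0.47 are untouched.

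**What to change.** The investigator should confirm the OGTT load and its unit, state it once, and make the Assessment of IR paragraph and item 2 of the procedures section agree with it. No load is proposed here, and neither passage should be treated as the reference until the investigator has confirmed the amount. The cost is a short text correction to the protocol. No hypothesis, endpoint definition, statistical model, sample size or power figure has to change.

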**viii. Description of Population to be Enrolled:**

Participants: This pilot study would allow for preliminary data collection on up to 30 obese adolescents (15 male, 15 female).

Recruitment: Participants will be recruited from adolescent, obesity and community clinics.

Subject Criteria:

*Inclusion criteria:*

- 1) High school students between the age of 15-19 years (the peak developmental period for delayed circadian phase);
- 2) BMI >90th percentile for age and sex;
- 3) Tanner stage 2 or greater.

*Exclusion criteria:*

- 1) Any medications that affect IR or sleep (e.g., metformin, hormonal contraception, stimulants, atypical antipsychotics);
- 2) regular use of melatonin or other sleep aids;
- 3) a prior diagnosis of obstructive sleep apnea, diabetes (HbA1c > 6.5), liver disease other than non-alcoholic fatty liver disease, pregnancy or breastfeeding;
- 4) IQ<70 or severe mental illness that may impact sleep (e.g., schizophrenia, psychotic episodes), verified through chart review;
- 5) teens not enrolled in a traditional high school academic program (e.g., home school students);
- 6) night shift employment;
- 7) travel across more than two time zones in the month prior to the study.

Informed Consent Plan: Appropriately qualified and informed personnel who have completed the COMIRB and HIPPA course requirements will fully explain the study protocol and consent form to the subject and guardian verbally in the language they understand. The explanation will be conducted in a quiet environment with adequate time given for the subject and guardian to review the study procedure before the commencement of the study. Asking the subject to explain the study in their own words will assess the subject's understanding. If non-English speaking subjects are enrolled in the study, the investigators will adhere to Section 10C of the COMIRB Instructions for Clinical Investigators regarding the consent of these subjects. The qualified personnel mentioned above will then obtain written consent from the guardian and assent from the subject, co-signed on the consent form, or in subjects who are 18 years or older, direct consent. The PI will make a good faith effort to obtain both parent signatures. The subject and guardian will be provided a copy of the consent form for better understanding and record purposes.

Special Consent/Accent Plan: Consent will be obtained from all participants in the study. Following explanation, all subjects below 18 years old will co-sign the consent form in addition to the parents signing the consent form. All subjects age 18 or older will sign the standard consent form.

Subject Compensation, Incentives & Rewards

Subjects will be compensated with Greenphire debit card payments during each scheduled visit. Participants will receive \$5 for the initial visit that includes signing consent and receiving the actigraphy watch. After completing the screening visit, consisting of OGTT, and questionnaires, participants will receive \$50 loaded on to a debit card. Participants will receive \$100 on the debit card following the overnight study visit. Compensation for all completed visits will total \$155.

### **Study Design and Research Methods**

Study Timeline: Participants will have 3 visits: an initial visit, a screening visit, and an overnight study visit. The initial visit will include informed consent and assent and receiving an actigraphy watch and instructions. The screening visit will include questionnaires, 3-hour frequently sampled oral glucose tolerance test (OGTT), and fasting labs to check for other components of metabolic syndrome. During the overnight study visit subjects will be admitted to the Children's Hospital Clinical research center inpatient unit from 4PM Thursday or Friday to 12PM the following day for salivary melatonin collection. During the entire protocol, teens will be asked to abstain from caffeine, non-steroidal anti-inflammatory drugs, marijuana, high carbohydrate meals, and alcohol.

Initial visit and sleep/wake monitoring: The initial visit will last approximately 30 minutes and will include consent and assent. Participants will be provided an actigraphy watch to monitor typical home sleep patterns. The Spectrum sleep/wake monitor (Phillips Resperonics, Bend, OR) will be worn on the non-dominant wrist and will collect data on movements in 1-min bins. The watch will be worn for the 7 days preceding the initial visit and participants will complete a concurrent sleep diary emailed to them each morning via RedCap to allow for removal of artifacts (e.g., failure to wear the actigraphy watch during a portion of the night). If participants have not completed the sleep diary by mid-morning, a RedCap email and text message reminder will be sent. The text messages will be generic so as not to identify the participant or that they are part of a research study. If participants do not have email or computer access, they can complete a paper/pencil sleep diary.

Screening visit and sleep/wake monitoring: The screening visit will last approximately 4 hours and will ideally occur on Thursdays or Fridays in order to be consistent with the amount of accumulated sleep debt incurred over the week. Menstruating girls will be scheduled in the follicular phase when possible, as menstrual timing can influence measures of IR. Participants will receive or be mailed an actigraphy watch to wear for 7 days prior to the overnight study visit while filling out a concurrent sleep diary.

Teens will follow a self-selected sleep schedule during the pre-study week, but data collection will take place during the academic year to capture participants' typical sleep schedule. Data will not be collected during the week following daylight savings changes or in a week following travel across one or two time zones. Average sleep start and end time, sleep duration, and sleep efficiency will be measured.

### **Description, Risks and Justification of Procedures and Data Collection Tools:**

#### **1. Blood Sampling**

**Description:** Blood will be drawn using a peripheral IV for HbA1c, ALT/AST, sex hormone binding globulin, a cholesterol panel, CRP, leptin, and adiponectin, and OGTT.

**Risk:** Minimal. Risk of pain, bruising at site of blood draw, excessive amount of blood

**Minimizing Risk:** The study involves sampling blood at multiple time points, thus an IV is needed to avoid multiple needle sticks. Proper sterile techniques will be used with blood draws and IV placement to decrease infection risk. EMLA cream will be used if subject desires to minimize pain of IV. The routine guidelines in our Pediatric CTRC are 2.5ml/kg for a single draw and no more than 5ml/kg over a 4 week period. For this study, the baseline labs will include 13 ml of blood and the OGTT includes 29ml of blood. Thus, our study visit is within the NIH Clinical Center guidelines of 9ml/kg in 6-8 weeks and within Children's Hospital Colorado's institutional guidelines of 5 ml/kg. We will use a minimum weight cutoff of 38 kg to remain below the most conservative pediatric CTRC blood drawing guidelines. Finally, our CTRC has a system to track other studies subjects might enroll in, and we ask during our consent process if the subject has been involved in any other studies in the past 6 weeks to avoid excessive blood drawing.

**Justification:** These labs are to measure for components of the metabolic syndrome, and to assess the primary study endpoint, IR. A hemoglobin A1c can be used to rule out diabetes.

